3.6.2.2 Physical Examination and Vital Sign Assessments

3.6.2.2.1 Physical Examination

The complete physical examination at the last scheduled visit of the prior double-blind phase 3 trial will serve as the screening/baseline physical examination for the current protocol. A complete physical examination will consist of a review of the following body systems: HEENT, thorax, abdomen, urogenital, extremities, neurological, and skin and mucosae. Repeat measurement of height is not required during Trial 331-10-238 if a Screening/Baseline value is available from the prior double-blind phase 3 trial. Waist circumference will be measured at Screening/Baseline, Week 14, and Week 26/ET. The following procedures will aid in the standardization of these measurements:

- The subject should be minimally clothed (ie, lightweight clothing; no heavy overgarments).
- Waist circumference should be recorded before a subject's meal and at approximately the same time at each visit.
- Measurement will be accomplished by locating the upper hip bone and the top of the right iliac crest and placing a weighted measuring tape in a horizontal plane around the abdomen at the level of the crest. Before reading the tape measure, the assessor should assure that the tape is snug, but does not compress the skin, and is parallel to the floor. The measurement is to be made at the end of a normal exhalation.²⁴

The principal investigator or his/her appointed designee is primarily responsible to perform the physical examination. If the appointed designee is to perform the physical examination, he/she must be permitted by local regulations and his/her name must be included on the FDA Form 1572. Whenever possible, the same individual should perform all physical examinations. Any condition present at the post-treatment physical examination that was not present at the screening/baseline examination should be documented as an AE and followed to a satisfactory conclusion.

3.6.2.2.2 Vital Signs

Vital sign measurements will include body weight, body temperature, systolic blood pressure (SBP), diastolic blood pressure (DBP), and heart rate. The following guidelines will aid in the standardization of body weight measurements:

- The same scale should be used to weigh a given subject each time, if possible.
- Scales should be calibrated and reliable; scales should be at zero just prior to each subject's weigh-in session.
- A subject should void prior to being weighed and be minimally clothed (ie, no shoes or heavy overgarments).
- Weight should be recorded before a subject's meal and at approximately the same time at each visit.

Blood pressure and heart rate measurements will be made in the supine, sitting, and standing positions after the subject has been in each position for at least 3 minutes. The supine measurements will be performed first, followed by sitting, and finally standing. Vital signs scheduled at the same visit as blood samples are to be completed before blood is drawn.

Subjects with uncontrolled hypertension (Screening/Baseline DBP > 95 mmHg) or symptomatic hypotension are excluded from the trial as are subjects with orthostatic hypotension defined as a decrease of ≥ 30 mmHg in SBP and/or a decrease of ≥ 20 mmHg in DBP after at least 3 minutes standing compared to the previous supine blood pressure **OR** development of symptoms (see [Table 3.4.3-1](#)). In addition, subjects should be excluded if they have any other vital sign measurement at Screening/Baseline that, in the investigator's judgment, is medically significant in that it would impact the safety of the subject or the interpretation of the trial results. However, any abnormal screening/baseline vital sign result(s) considered to be clinically significant should be repeated to confirm the finding(s) before excluding the subject from the trial. [Appendix 3](#) is included to assist investigators in their assessments of results that may be potentially

medically significant, depending on the subject's medical history and clinical presentation.

3.6.2.3 ECG Assessments

Twelve-lead ECGs will be recorded at the visits specified in [Table 3.6-1](#). ECG recordings will be obtained after the subject has been supine and at rest for at least 5 minutes. Additional 12-lead ECGs may be obtained at the investigator's discretion and should always be obtained in the event of an early termination. A central ECG service will be utilized for reading all ECGs in order to standardize interpretations for the safety analysis. In addition, ECG results will be evaluated at the investigational site to monitor safety during the trial. The principal investigator or qualified designee will review, sign, and date each ECG reading, noting whether or not any abnormal results are of clinical significance. The ECG will be repeated if any results are considered to be clinically significant.

As the results from the central reader will not be available at the Screening/Baseline visit, the subject will be enrolled into Trial 331-10-238 based on the local ECG results. A screening/baseline ECG finding of QTc corrected for heart rate by Fridericia's formula (QTcF) \geq 450 msec is exclusionary (see [Table 3.4.3-1](#)). In addition, subjects should be excluded if they have any other abnormal ECG finding at Screening/Baseline that, in the investigator's judgment, is medically significant in that it would impact the safety of the subject or the interpretation of the trial results. However, any screening/baseline ECG with abnormal result(s) considered to be clinically significant should be repeated to confirm the finding(s) before excluding the subject from the trial. [Appendix 5](#) is provided as a guide for determining potentially clinically relevant ECG abnormalities. If the results from the central reader, when available, indicate a screening/baseline QTcF \geq 450 msec, the investigator must contact the medical monitor to discuss the subject's continued participation in the trial.

3.6.2.4 Other Safety Assessments

It is required that a trained and experienced clinician administer the safety assessments, including the EPS scales (SAS, AIMS, and BARS) and C-SSRS. The number of raters within each trial center should be kept to a minimum. All efforts will be made to ensure that the same clinician administers the scales for a given subject. Notations in the subject's trial records should substantiate the ratings. Training and materials for rating will be provided by Bracket.

3.6.2.4.1 Simpson Angus Scale (SAS)

The SAS²⁵ ([Appendix 10](#)) consists of a list of 10 symptoms of Parkinsonism (gait, arm dropping, shoulder shaking, elbow rigidity, wrist rigidity, head rotation, glabella tap, tremor, salivation, and akathisia). Each item will be rated on a 5-point scale, with a score of zero representing absence of symptoms, and a score of 4 representing a severe condition. The SAS Total Score is the sum of the scores for all 10 items.

Anticholinergics, propranolol, benzodiazepines, and non-benzodiazepine sleep aids are not permitted within 12 hours of scale administration (see [Section 4](#)). Investigators are encouraged to delay scale administration until 12 hours have elapsed, if at all possible. However, if delaying administration of the scale is not feasible, the SAS should still be administered and the use of the medication documented, including a notation of the drug name, dose, and time of administration on the electronic case report form (eCRF).

3.6.2.4.2 Abnormal Involuntary Movement Scale (AIMS)

The AIMS²⁶ assessment ([Appendix 11](#)) consists of 10 items describing symptoms of dyskinesia. Facial and oral movements (items 1 through 4), extremity movements (items 5 and 6), and trunk movements (item 7) will be observed unobtrusively while the subject is at rest (eg, in the waiting room), and the investigator will also make global judgments on the subject's dyskinesias (items 8 through 10). Each item will be rated on a 5-point scale, with a score of zero representing absence of symptoms (for item 10, no awareness), and a score of 4 indicating a severe condition (for item 10, awareness, severe distress). For this scale, the subject is to be sitting on a hard, firm chair. In addition, the AIMS includes two yes/no questions that address the subject's dental status. Anticholinergics, propranolol, benzodiazepines, and non-benzodiazepine sleep aids are not permitted within 12 hours of scale administration (see [Section 4](#)). Investigators are encouraged to delay scale administration until 12 hours have elapsed, if at all possible. However, if delaying administration of the scale is not feasible, the AIMS should still be administered and the use of the medication documented, including a notation of the drug name, dose, and time of administration on the eCRF.

The AIMS Movement Rating Score is defined as the sum of items 1 through 7 (ie, items 1 through 4, facial and oral movements; items 5 and 6, extremity movements; and item 7, trunk movements).

3.6.2.4.3 Barnes Akathisia Rating Scale (BARS)

The BARS²⁷ ([Appendix 12](#)) consists of 4 items related to akathisia: objective observation of akathisia by the investigator, subjective feelings of restlessness by the

subject, subjective distress due to akathisia, and global clinical assessment of akathisia. The first 3 items will be rated on a 4-point scale, with a score of zero representing absence of symptoms and a score of 3 representing a severe condition. The global clinical evaluation will be made on a 6-point scale, with zero representing absence of symptoms and a score of 5 representing severe akathisia. To complete this scale, subjects will be observed while they are seated and then standing for a minimum of 2 minutes in each position. Symptoms observed in other situations (eg, while engaged in neutral conversation or engaged in other activity) may also be rated. Subjective phenomena are to be elicited by direct questioning. Anticholinergics, propranolol, benzodiazepines, and non-benzodiazepine sleep aids are not permitted within 12 hours of scale administration (see [Section 4](#)). Investigators are encouraged to delay scale administration until 12 hours have elapsed, if at all possible. However, if delaying administration of the scale is not feasible, the BARS should still be administered and the use of the medication documented, including a notation of the drug name, dose, and time of administration on the eCRF.

The BARS Global Score is defined as the global clinical assessment of akathisia.

3.6.2.4.4 Suicidality

Suicidality will be monitored during the trial using the C-SSRS. Subjects completed the “Baseline/Screening” C-SSRS form at the beginning of the prior double-blind phase 3 trial; therefore, only the “Since Last Visit” C-SSRS form will be used in Trial 331-10-238. A copy of the “Since Last Visit” C-SSRS form is provided in [Appendix 13](#).

3.6.2.4.5 Sexual Function

The MSFQ²⁸ is a measure of a subject’s self-reported sexual functioning. It consists of 5 items that are each rated as one of six defined grades of functioning ([Appendix 14](#)). The investigator or designated trial personnel should ensure that a subject completes this instrument completely and legibly.

3.6.3 Efficacy Assessments

It is required that appropriately trained and qualified individuals administer the CGI-S and CGI-I. The number of raters within each trial center should be kept to a minimum. All efforts will be made to ensure that the same clinician administers the scales for a given subject. Notations in the subject’s trial records should substantiate the ratings. Training and materials for rating will be provided by Bracket.

3.6.3.1 Clinical Global Impression - Severity of Illness Scale (CGI-S)

The severity of illness for each subject will be rated using the CGI-S.²⁶ To perform this assessment, the rater or investigator will answer the following question: "Considering your total clinical experience with this particular population, how mentally ill is the patient at this time?" Response choices include: 0 = not assessed; 1 = normal, not at all ill; 2 = borderline mentally ill; 3 = mildly ill; 4 = moderately ill; 5 = markedly ill; 6 = severely ill; and 7 = among the most extremely ill patients. A sample of the CGI-S is provided in [Appendix 6](#).

3.6.3.2 Clinical Global Impression - Improvement Scale (CGI-I)

The efficacy of trial treatment will be rated for each subject using the CGI-I.²⁶ The rater or investigator will rate the subject's total improvement whether or not it is due entirely to drug treatment. All responses will be compared to the subject's condition at Screening/Baseline (ie, last scheduled visit of the prior double-blind phase 3 trial). Response choices include: 0 = not assessed, 1 = very much improved, 2 = much improved, 3 = minimally improved, 4 = no change, 5 = minimally worse, 6 = much worse, and 7 = very much worse. A sample of the CGI-I is provided in [Appendix 7](#).

3.6.3.3 Subject Assessment Recording

3.6.3.3.1 Sheehan Disability Scale (SDS)

The SDS^{29,30} is a self-rated instrument used to measure the effect of the subject's symptoms on work/school, social life, and family/home responsibilities ([Appendix 8](#)). The SDS is a visual analogue scale that uses spatio-visual, numeric, and verbal descriptive anchors simultaneously to assess disability across the three domains. The number most representative of how much each area was disrupted by symptoms is marked along the line from 0 = not at all, to 10 = extremely. Scores of 5 and above are associated with significant functional impairment. In addition to the visual scale, the SDS includes two questions related to productivity losses due to the psychiatric symptoms and impairment.

3.6.3.3.2 Inventory of Depressive Symptomatology (Self-Report)

The IDS-SR³¹ is a 30-item self-report measure used to assess core diagnostic depressive symptoms as well as atypical and melancholic symptom features of MDD ([Appendix 9](#)). The investigator or designated trial personnel should ensure that a subject completes this instrument completely and legibly.

3.6.3.3.3 Resource Utilization Form (RUF)

The RUF is a self-report tool designed to collect information regarding the extent of medical care sought by subjects while participating in the trial ([Appendix 15](#)). The number of hospitalizations and days of hospitalization within the past 12 months will be collected on the Baseline Form at Screening/Baseline, including any hospitalizations that may have occurred during the subject's participation in the prior double-blind phase 3 trial. The number of visits to various practitioners for mental health and other reasons within the 3 months prior to Screening/Baseline (excluding any visits from the prior double-blind phase 3 trial) will be collected on the Baseline Form and the number of such visits occurring during the trial (excluding visits related to the trial) will be collected on the Follow-up Form at Week 26/ET.

3.6.4 End of Trial

The End of Trial Date is defined as the last Date of Contact or the Date of Final Contact Attempt from the Post-treatment Follow-up eCRF page for the last subject completing or withdrawing from the trial.

3.7 Stopping Rules, Withdrawal Criteria and Procedures

3.7.1 Entire Trial or Treatment Arm(s)

If the sponsor terminates or suspends the trial for safety or unanticipated other reasons, prompt notification will be given to investigators, IRBs/IECs, and regulatory authorities in accordance with regulatory requirements.

3.7.2 Individual Center

A particular center may be terminated from the trial at the discretion of the investigator, sponsor, or IRB, eg, for non-enrollment of subjects or noncompliance with the protocol. The investigator will notify the sponsor promptly if the trial is terminated by the investigator or the IRB/EC at the site.

3.7.3 Individual Subject

If a subject discontinues from the trial prematurely, the reason must be fully evaluated and recorded appropriately in source documents and the eCRF. If the subject is being withdrawn because of an AE, that AE should be indicated as the reason for withdrawal. All subjects have the right to withdraw at any point during treatment without prejudice. The investigator can discontinue a subject's participation in the trial at any time if

medically necessary. In addition, subjects meeting the following criteria must be withdrawn from the trial:

- a) occurrence of any AE, intercurrent illness or abnormality in a laboratory assessment which, in the opinion of the investigator, warrants the subject's permanent withdrawal from the trial;
- b) treatment with a prohibited concomitant medication other than the use of appropriate medications for the treatment of AEs under direction of the investigator;
- c) subject noncompliance, defined as refusal or inability to adhere to the trial schedule or procedures (see [Section 3.11](#), Subject Compliance);
- d) at the request of the subject, investigator, sponsor or designee, or regulatory authority;
- e) subject becomes pregnant;
- f) subject cannot tolerate the minimum dose of brexpiprazole (ie, 0.5 mg/day), the minimum protocol-defined therapeutic dose of ADT (see [Table 3.2.1.2-1](#)), or requires a different ADT; or
- g) subject is lost to follow-up.

The investigator will notify the sponsor promptly when a subject is withdrawn. Subjects withdrawn prior to Week 26 must complete the Week 26/ET evaluations at the time of withdrawal. In addition, all subjects who withdraw prematurely from the trial will be assessed 30 (+ 2) days after the last dose of IMP for evaluation of safety. This assessment can be accomplished via telephone contact or clinic visit at the investigator's discretion. Withdrawn subjects will not be replaced.

3.8 Screen Failures

A screen failure subject is one from whom informed consent is obtained and is documented in writing (ie, subject signs an ICF), but who is not started on treatment, whether through randomization or open assignment. For the purposes of Trial 331-10-238, treatment begins with the first dose of open-label brexpiprazole in the Treatment Phase. Subjects who do not qualify for Trial 331-10-238 at the last scheduled visit of the prior double-blind phase 3 trial may not be rescreened.

3.9 Definition of Completed Subjects

The treatment period is defined as the time period during which subjects are evaluated for primary and/or secondary objectives of the trial irrespective of whether or not the subject actually consumed all doses of IMP. Subjects who are evaluated at the last scheduled

visit during the treatment period will be defined as trial completers. For purposes of this trial, subjects who complete the Week 26 visit will be defined as completers. Protocol-specified post-treatment follow-up contacts will not qualify as the “last scheduled visit.” Subjects who are not completers are defined as those who “discontinued the trial.”

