3.10 Definition of Lost to Follow-up

Subjects who cannot be contacted on or before the Week 26 visit during the treatment period and who do not have a known reason for discontinuation (eg, withdrew consent or AE) will be classified as “lost to follow-up” as the reason for discontinuation. The site will make three attempts to contact the subject by telephone and in the event the site is unable to reach the subject by telephone, the site will attempt to contact the subject via certified mail or an alternative similar method where appropriate.

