Appendix 7, Clinical Global Impression - Improvement Scale (CGI-I), Sentence 2:

Rate total improvement whether or not in your judgment it is due entirely to drug treatment. Compared to his/her condition at the last *scheduled* visit of ***the prior double-blind phase 3 trial Trial 331-10-227 or Trial 331-10-228*** (ie, prior to enrollment into Trial 331-10-238), how much has patient changed?

ADDITIONAL RISK TO THE SUBJECT:

There is no additional risk to the subjects as a result of this protocol amendment.

Amendment Number: 3

Issue Date: 11 Apr 2014

PURPOSE:

The sponsor has determined the need for a third formal amendment to the original protocol. Due to a well-established safety profile in the completed double-blind and long-term Phase 2 and Phase 3 trials the study duration has been reduced from 52 weeks to 26 weeks and the number of assessments has been decreased. In addition, administrative clarifications were made, including changes to text to enhance readability and consistency and correct typographical errors. The purpose of amending Protocol 331-10-238, issued on 16 Nov 2012 (amendment 2), was to:

- reduce the trial duration from 52 weeks to 26 weeks.
- reduce the number of visits to match the reduction in trial duration.
- minimize safety assessments performed at each visit.
- reduce the safety scale administration performed at each visit.
- reduce the efficacy scale administration performed at each visit.
- make administrative changes.

BACKGROUND:

Due to a well-established safety profile in the completed double-blind and long-term Phase 2 and Phase 3 trials the study duration has been reduced from 52 weeks to 26 weeks and the number of assessments has been decreased. In addition, administrative clarifications were made, including changes to text to enhance readability and consistency and correct typographical errors.

MODIFICATIONS TO PROTOCOL:

General Revisions:

- Changes made to Protocol 331-10-238 in this third amendment are as outlined above.
- All the references to Week 52 were changed to Week 26. The word “study” was replaced by “trial” throughout the document.
- All visits and assessments from Week 26 to Week 52 were removed.
- Reference to Trial 331-13-214 was added wherever Trial 331-10-227 and Trial 331-10-228 were referred. .
- Sections 8.5 to 8.5.4 (Reporting of Product Quality Complaints) were added.

General Revisions:

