3.1 Type/Design of Study

3.1.1 Trial Design Before Protocol Amendment 3

This is a multicenter, **52-week**, open-label trial designed to assess the long-term safety, tolerability, and efficacy of adjunctive brexpiprazole in depressed adults on concurrent antidepressant therapy (ADT). The trial will be conducted on an outpatient basis.

Enrollment into the trial will be drawn from eligible subjects who have completed one of the double-blind, phase 3 brexpiprazole MDD trial and who, in the investigator's judgment, could potentially benefit from adjunctive treatment with oral brexpiprazole for MDD. A schematic of the study design is presented in [Figure 3.1-1](#).

The trial will be organized as follows:

Screening/Baseline: Subjects will be screened for eligibility at the last scheduled visit of the prior double-blind phase 3 trial. Subjects will sign a separate informed consent form (ICF) for participation in Trial 331-10-238 before any procedures specific to the open-label trial are performed. The assessments from the last scheduled visit of the prior double-blind phase 3 trial will serve as the baseline measures for Trial 331-10-238 for any assessment that is not unique to the open-label trial. Medical history will be updated, if necessary.

Treatment Phase: Eligible subjects will receive daily treatment with open-label brexpiprazole and ADT as described in the Investigational Medicinal Product (IMP), Dose, Formulation, Mode of Administration section. Visits will occur at the end of

Weeks 1, 2, 4, 8, 14, 20, 26 32, 28, 44, and 52. All subjects will receive up to 52 weeks of open-label treatment in Trial 331-10-238.

Follow-up: Subjects will be followed up for safety via telephone contact or clinic visit 30 (+ 2) days after the last dose of open-label medication.

[figure not shown]

Figure 3.1-1 Trial Design Schematic

3.1.2 Trial Design After Protocol Amendment 3

This is a multicenter, **26-week**, open-label trial designed to assess the long-term safety, tolerability, and efficacy of adjunctive brexpiprazole in depressed adults on concurrent antidepressant therapy (ADT). The trial will be conducted on an outpatient basis. Enrollment into the trial will be drawn from eligible subjects who have completed one of the double-blind, phase 3 brexpiprazole MDD trial and who, in the investigator's judgment, could potentially benefit from adjunctive treatment with oral brexpiprazole for MDD. A schematic of the study design is presented in [Figure 3.1-2](#).

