6.1 Subject Disposition, Completion Rate and Reasons for Discontinuation

Subject disposition will be summarized for the Enrolled Sample.

Subject completion rate by week, and reasons for discontinuation will be summarized for the Enrolled Sample. In addition, these summaries will also be done by ADT

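### Applied literally, Protocol 3.9 would class 52-week enrollers who withdrew after Week 26 as completers, and SAP 6.1 sets no cohort-specific rule to prevent it

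*Protocol*

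**What the plan says.** Protocol 3.9 first gives a general rule that depends on the end of the treatment period ("Subjects who are evaluated at the last scheduled" visit of that period are completers). It then fixes the rule for this trial: "For purposes of this trial, subjects who complete the Week 26 visit will be defined as completers". Anyone else has discontinued; the sentence begins "Subjects who are not completers are defined as those who". Section 3.10 ties loss to follow-up to the same visit: "Subjects who cannot be contacted on or before the Week 26 visit during the treatment period", with no known reason for leaving.

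The wording comes from Amendment 3, whose change log in Protocol Appendix 16 records that "All the references to Week 52 were changed to Week 26". Under the transition rules (Protocol 3.6.1.8 and Table 3.6-1, footnote b), ongoing subjects short of Week 26 were to be re-consented and end there. Those already past Week 26 were to have the Week 26/ET procedures at their next scheduled visit.

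The SAP keeps the earlier design alive for analysis. SAP 3.1.1 says of it: "All subjects will receive up to 52 weeks of open-label treatment in Trial 331-10-238". SAP 5.1 splits all summaries into all subjects, 52-week enrollers and 26-week enrollers. SAP 6.1 says: "Subject completion rate by week, and reasons for discontinuation will be summarized for the Enrolled Sample". SAP 13 lists disposition (CT-1.1), completion rate (CT-1.2) and reasons for discontinuation (CT-2.1, and CT-2.2 by ADT) for each of the three groups. The SAP defines neither completer nor discontinued.

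**The concern.** The only completer definition in either document is fixed at Week 26, while one of the two reporting cohorts was treated under a plan that ran to Week 52. Consider a 52-week enroller who attended Week 26 and withdrew at Week 40. By the trial-specific sentence of 3.9 this subject is a completer, so has not discontinued, and has no place in a table of discontinuation reasons. A subject lost at Week 35 would not meet the current wording of 3.10 either.

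At stake is the description of longer-term retention: how many 52-week enrollers completed, and why the others left. If the withdrawal was for a TEAE, the subject would be a completer in CT-2.1 and a discontinuation in CT-8.6. If it was for another reason, such as withdrawn consent or loss to follow-up, the SAP lists no other table in which that reason would be summarized.

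**Working it through.** **Check of the definitions.** There is no figure in the plan to reproduce. The check is to run each candidate rule over the kinds of subject that the 52-week cohort can contain under the documents.

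| 52-week enroller | Week 26 rule (3.9 read literally) | Uniform Week 52 rule | What happened |
|---|---|---|---|
| A. Withdrew before Week 26 | Discontinued | Discontinued | Withdrew |
| B. Attended Week 26, withdrew before Week 52 for own reasons | **Completer** | Discontinued | Withdrew |
| C. Past Week 26 at Amendment 3, ended at next scheduled visit | Completer | **Discontinued**, unless that visit was Week 52 | Ended by the amendment |
| D. Not yet at Week 26 at Amendment 3, ended at Week 26 | Completer | **Discontinued** | Ended by the amendment |
| E. Attended Week 52 | Completer | Completer | Completed |

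The Week 26 rule misplaces group B. The Week 52 rule misplaces group D and most or all of group C. No single week works for this cohort, or for the all-subjects tables that include it.

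**Size, by illustration only.** The documents give no dropout or retention figure. Assume a constant monthly withdrawal m over the six months from Week 26 to Week 52. The share w of those followed through that period who withdraw is

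w = 1 − (1 − m)^6

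- m = 1%: 1 − 0.99^6 = 1 − 0.9415 = 5.9%
- m = 3%: 1 − 0.97^6 = 1 − 0.8330 = 16.7%

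To see what this does to the tables, let c be the share of the cohort that reaches Week 26, also assumed. Ignore groups C and D, so that all who reach Week 26 are followed towards Week 52. Completion is c under the Week 26 rule and c(1 − w) under the Week 52 rule. The overstatement is c × w, and the share of all discontinuations left out of the reasons table is c × w / [1 − c(1 − w)].

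- Low end, c = 0.60, w = 0.0585: overstatement 0.60 × 0.0585 = 3.5 percentage points; share left out 0.0351 / (1 − 0.5649) = 8%.
- High end, c = 0.80, w = 0.1670: overstatement 0.80 × 0.1670 = 13.4 percentage points; share left out 0.1336 / (1 − 0.6664) = 40%.

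Every subject in groups C or D makes the overstatement smaller than these values, because that subject had less time, or none, in which to withdraw after Week 26.

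**The case against.** The strongest reply is that the documents leave the rule open rather than misstate it. SAP 6.1 does not cite Protocol 3.9, and nothing says that CT-1.x and CT-2.x use its Week 26 sentence. The general sentence just before it points to the last scheduled visit, which under the earlier design is Week 52. SAP 1 says all amendments were considered, SAP 8 gives the last visit as either Week 26 or Week 52 (or early termination), and the visit windows in SAP 11.1 run to Week 52. Subjects who left before Amendment 3 did so under text that referred to Week 52, so the subject lost at Week 35 was covered at the time.

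Much of this stands. A reader might infer that late withdrawals *are* counted as completers in the tables; the documents support only that they *would be* if 3.9 is applied literally. A reader might also infer that late withdrawals for adverse events vanish from the report. They do not: Protocol 3.7.3 requires the reason to be recorded whenever a subject leaves early, and CT-8.6 and CT-9.3 present discontinuations due to adverse events for 52-week enrollers. Completion by week may show attrition after Week 26 whichever label is used. Nor is the primary outcome touched: Protocol 3.5.1 rests it on the frequency and severity of adverse events, and no incidence changes.

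Three things remain. The Week 26 sentence directly follows the general rule and makes it specific, so it is the natural one for a programmer to use. The Week 52 reading does not rescue the plan, because of groups C and D, and the SAP is not uniform on it (SAP 9.8 names Week 52 alone as the last visit). By-week completion shows that subjects left, but not why.

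**Conclusion.** The point holds in conditional form. The stated completer rule does not fit the 52-week cohort, the SAP supplies no other, and neither fixed-week rule classifies the cohort correctly. The harm is confined to the disposition, completion and discontinuation-reason tables for 52-week enrollers and all subjects. It is most serious for withdrawals not due to adverse events, whose reasons have no other planned summary.

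The size is unknown. The 5.9% to 16.7% depends wholly on the assumed 1% to 3% monthly withdrawal. It applies only to those who reached Week 26 and were followed to Week 52, a number the documents do not give. It is not an error rate for the whole cohort or for all subjects. The correction is cheap and worth making.

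**What to change.** In SAP 6.1, define completion by the duration in force for each subject, using subject-level re-consent, visit and eCRF disposition records:

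- Participation ended under the 52-week design: completer if the Week 52 visit was attended.
- Participation ended under Amendment 3: completer if the Week 26/ET procedures were done at Week 26, or at the next scheduled visit because of the amendment. Show those stopped after Week 26 on a separate line, labelled *completed, shortened by Amendment 3*.
- Any other withdrawal, at any week: discontinuation with its eCRF reason, including loss to follow-up after Week 26.

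Apply this in CT-1.x and CT-2.x for 52-week enrollers and all subjects, and reconcile the adverse-event withdrawals with CT-8.6 and CT-9.3.

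The rule should not depend on a site-level date for Amendment 3, because nothing in the documents shows that such a date is in the database. Re-consent is stated only for subjects who had not reached Week 26, so for those already past it the visit and disposition records must carry the classification. The cost is SAP wording, one derived variable and a slightly lower stated completion rate, with no change to trial conduct.
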